We have performed a pilot study at one REDS-II Center in Pittsburgh which showed that 30% of patients (weighted by size of institution and transfusion volume) have a chest x-ray within 12 hours. The rate is 42% for a 24-hour interval and 52% for a 48-hour interval. Because the consensus definition of TRALI requires a chest x-ray result, and symptoms of TRALI must occur within 6 hours of the transfusion, we believe that an interval of 24 hours, "the planned interval for this protocol" will balance sensitivity and specificity in identifying TRALI cases. The 24-hour interval has also been employed in recent studies in which findings on chest x-ray taken the next day (Finlay et al.) or within 24 hours of transfusion (Higgins S et al.) were included to arrive at a diagnosis of TRALI. This approach will limit our ability to detect mild cases which do not have a chest x-ray and thus do not meet a definition of TRALI. Those cases which have a chest x-ray done more than 24 hours after the transfusion will also be missed. Despite these limitations, our study design clearly includes collection of data that permit us to make a diagnosis of TRALI according to the generally accepted consensus criteria and therefore, we will not be missing a TRALI diagnosis in any significant number of cases.

Further, to help accurately identify TRALI in our study, we are proposing to create a medical review board. Gajic et al. conducted a retrospective medical chart review and found that 60 patients (of a total of 181) had developed acute lung injury after transfusion (Gajic O et al.). In this study, the inter-observer agreement for the diagnosis of acute lung injury was moderate (kappa 0.6) and the final diagnosis had to be assigned using a consensus mechanism when differences existed. Therefore, for our study, we propose to create a medical review board that will be responsible for reviewing data extracted from medical charts and determining if a given case meets the criteria for a diagnosis of TRALI or not. The board will be blinded as to the recipient group (i.e., the board members will not know whether the recipient received at least one known HLA antibody-positive component, or one known HLA antibody-negative component). The board will be composed of physicians from the subspecialties of critical care, pulmonary medicine and intensive care.

G2. Two Consensus Definitions of TRALI: The Finlay study estimated TRALI risk by including TRALI cases with and without other risk factors for acute lung injury (ALI) based upon diagnostic criteria that were developed by the NHLBI Working Group. Another consensus definition has been developed by the Canadian Consensus Conference Group which classified "TRALI with other risk factors for ALI" as "possible TRALI". For research purposes, we believe that in order to better characterize the incidence of TRALI (and not underestimate it), we should include "TRALI cases with other risk factors for ALI" when estimating our overall TRALI incidence. The identification of all possible TRALI cases would give the health care professional a more accurate picture of the potential for TRALI and will allow better decisions concerning the costs and benefits associated with various preventive steps that may be envisioned. Our data collection form will permit classification by both the Canadian Consensus Conference and the NHLBI working group criteria and will permit a comparison of cases diagnosed by these two slightly different definitions.

G3. Generalizability of Finlay's data to the proposed study setting: Since certain blood components (e.g. Plasma, Apheresis Platelets) are more likely to cause TRALI, it is important to review whether the blood component mix transfused at UCSF Medical Center (47% were RBCs, 34% FFPs, 15% apheresis platelets, 4% others) is similar or not to what could be expected at hospitals associated with the REDS-II centers. We have therefore reviewed published data on blood component utilization for various types of hospitals. The data shown below in Table-10 include the results from the US Department of Health and Human Services (DHHS) which had funded a nationwide blood collection and utilization survey in 2005.

As shown in **Table-10**, the data from 2001 described by Novis et al. show that among small hospitals, platelet concentrates derived from whole blood continue to be used. However, these data are now seven years old and in the intervening period, the use of apheresis platelets has grown and that of platelet concentrates from whole blood has decreased nationally. The DHHS data (**Table-10**) provide evidence for this change in transfusion practice.

Another important aspect of Finlay's data includes the fact that FFP represented 34% of all components transfused. Since plasma volume in FFP is greater than that in red blood cells and in whole blood-derived platelets, the greater use of FFP in Finlay's patients might have contributed to a higher risk for TRALI. We therefore compared the blood component usage in Finlay's patients to other published data.

FFP utilization as a proportion of total blood component transfusion is less in small hospitals (<200 beds) compared to Finlay's data which represents use in a large, university based, tertiary care hospital (Novis et al.). Assessed in another way, the ratio of FFP to RBC unit transfusion at UCSF Medical Center (Finlay et al.) was 1:1.4. For small hospitals, the ratio was 1:7.8 (Novis et al.). An average ratio of 1:3.6 has been reported (Wallis and Dzik).

The above data indicate that the ratio of FFP to RBC transfusion at Finlay's institution is higher than that for the US. Since FFP (including other transfusable plasmas) is more likely to cause TRALI than other types of blood products (e.g., red blood cells), and if more FFP units were transfused in Finlay's study than what would be expected at hospitals enrolling in our study, we may overestimate the number of recipients who may develop TRALI in our study if we base our estimates solely on Finlay's data. Therefore, we have used the recent data from the DHHS survey to calculate the estimated TRALI cases among control and case recipients.

In our estimates for number of patients needed for the study (control vs. case recipients), we assigned different weights of TRALI risk to the plasma rich products compared to the plasma poor products. We derived the numbers of needed study subjects based on incidence per number of units transfused with and without assigning any weights. In assigning a higher risk to the plasma-containing products, we have used the assumption that the risk with FFP (and other transfusable plasmas) and apheresis platelets is five to ten fold greater than the risk with red blood cells. This assumption is supported by recent data from the American Red Cross which show an odds ratio (relative to red cells) in fatal TRALI cases of 12.5 with the plasma-containing products and an odds ratio of 7.9 for apheresis platelets. The assumption is also biologically plausible in that the amount of plasma in the higher risk components is approximately six fold

greater than the amount in the lower risk components; i.e. each unit of FFP contains approximately 220-250 ml of plasma, each apheresis platelet transfusion contains 250-300 mL of plasma and a unit of red blood cells contains approximately 20-40 mL of plasma. Based on these considerations, we have calculated our sample size in different ways as described in the section on statistical considerations.

_ rabic-ro. blood component utilization by type of hospitals						
Study/Type	RBC	FFP	Apheresis	Whole	Other	Total units
of hospitals	transfused	transfused	Platelets	blood-		transfused
			transfused	derived		
				platelets		
				transfused		
US Dept	13,912,000	4,089,000	1,389,667*	1,537,000	1,079,000	22,006,667
HHS	(63%)	(19%)	(6%)	(7%)	(5%)	
(DHHS)						
Finlay	3258 (47%)	2319(34%)	1003(15%)	0	308(4%)	6888
(major						
academic)						
Novis	365263((73%)	47031(9%)	12829(3%)	75031(15%)	0	500,154
(small						
community						
<200 beds)						

 Table-10: Blood component utilization by type of hospitals

*The survey reported whole-blood derived platelet (WBDP) equivalents. Each apheresis platelet unit was assumed to be six WBDP units.

H. Statistical considerations

H1. Number of donors with and without HLA antibody and their donations/components: HLA antibody positives are those donors whose samples show a normalized background ratio (NBG) of 10.8 or higher in HLA Class I antibody testing and an NBG ratio of 6.9 or higher in HLA class II antibody testing by the Luminex method. These cut-offs represent a mean + 3 standard deviations of a log transformed distribution of values in non-transfused males enrolled in LAPS-I. There are 879 such donors at the five REDS centers which are more than sufficient for this study. If the number of confirmed positive antibody donors exceeds the capacity of the study to perform the record review, a selection procedure will need to be introduced. The number of LAPS donors without antibody will be even higher and will therefore not present a problem for the number needed for the study.

H2. Hospital participation rate: Assuming that the participating hospitals receive about 50% of blood components distributed by the REDS-II centers, a total of 2,590 blood components will be evaluated from antibody-positive donors and 2,590 blood components from antibody-negative donations. The number of components donated by the LAPS donors that would allow the total number of components (2,590 in each group) needed for the study is described in section F8 above.

H3. Assumptions underlying power considerations: We have assumed that about half of the donations are given by male donors and half by female donors with about 17% of the latter having HLA antibodies. We also assumed that 1% of male donors are HLA antibody positive. Thus, we assumed that about 9% of components received by a recipient on average are HLA antibody-positive. These numbers are supported by the recently analyzed data from LAPS-I in which 17.2% of female donors were HLA antibody positive as compared to 1% of male donors. They are further supported by three published studies. First, the study of 324 apheresis female donors showed a prevalence of HLA class I & II antibodies of 16.7% (Densmore 1999). Second, a study of 1416 UK blood donors (males and females) showed a prevalence of HLA class I & II antibodies (Bray et al. 2004). The results from the LAPS study indicate the prevalence will be about 9% in all (males plus females) donors.

We also further assumed that there will be only one study component transfused per patient and that there will not be new onset hypoxemia in any given patient more than once during the transfusion episode involving the study component.

Another assumption for the power calculation is that 80% of the TRALI cases result from leukocyte antibodies. This assumption is supported by the original studies of [name] reported in 1985. More recent data also support this assumption. For instance, antigen-antibody correspondence was demonstrated in 87% (13 of 15) of cases in one recent series (Kopko et al. 2002). An analysis of fatal TRALI cases reported to FDA also has demonstrated the presence of donor leukocyte antibodies in 83% (40 of 48) of the cases. (Holness L et al.).

Based on these assumptions and data from the study by Finlay et al., we estimate

- the probability of a HLA antibody-positive high risk component causing TRALI to be 1.59%
- the probability of a HLA antibody-negative component causing TRALI to be 0.04%
- the probability of a component of unknown HLA antibody status causing TRALI to be 0.18%

The Finlay data suggest a transfusion episode consists of 8 blood components per recipient. The number of subjects needed for the study decreases significantly if the number of blood components transfused per patient is less than 8.0 (i.e. there would be fewer components in the transfusion episode with unknown HLA status; these 'unknown' components 'muddy' the analysis). In order to determine the number of components per transfusion, data from the Pittsburgh hospitals were collected and analyzed. These data were collected for October 2006 for five hospitals that represent small and large community hospitals and a University Medical Center with trauma and transplant services. Data are shown below in **Table-11**.

unterent categories of nospitals located in 1 htsburgh area						
Hospital Category	# RBC	# Patients	Tot RBC /	Tot plasma/	Tot Plts/	Tot
	tx'd/yr	Analyzed (1	# per pt	#per pt	#per patient	components/#
	-	month data)				per pt
A. Small	3500	107	246/2.3	50/0.5	32/0.3	328/3.1
community						
B. Medium	7500	240	482/2.0	91/0.4	44/0.2	617/2.6
Community						
C. Large	11,000	301	868/2.9	633/2.1	1740/5.8	3241/10.8
community w						
cancer ctr						
D. Large	15,000	404	1175/2.9	621/1.5	580/1.4	2376/5.9
community						
E. (University	30,000	676	3066/4.5	1786/2.6	2196/3.2	7048/10.4
Trauma/trans-						
plant)						
Combined data		1728	5837/3.4	3181/1.8	4592/2.7	13610/7.9

Table-11. Number of blood components transfused during a hospital admission among different categories of hospitals located in Pittsburgh area

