C2. Secondary objectives: Secondary objectives will include the risk of TRALI associated with HLA antibodies in the presence and absence of HNA antibodies and HLA antibody characteristics such as HLA class I vs. class II, antibody strength (as indicated by signal intensity on the screening assay), and antibody specificity.

D. Hypotheses

D1. Estimation of TRALI in relation to number of blood components: Based on experience of Finlay et al. who performed detailed retrospective record review, and on additional assumptions outlined in G3 and H3, we hypothesize that the incidence of TRALI from high risk products is 7.1 per 1,000 HLA antibody-positive components, 0.45 per 1,000 HLA antibody-negative components, and 1.8 per 1,000 components of unknown HLA antibody status. It should be noted that Finlay et al. included TRALI cases with or without associated risk factors for acute lung injury in accordance with the NHLBI diagnostic criteria for TRALI as shown in Table-2 above.

D2. Estimation of TRALI in relation to number of recipients: Based on the experience of Finlay et al. who performed detailed retrospective record review, and on additional assumptions outlined in G3 and H3, we project that the incidence of TRALI (with and without other risk factors for ALI) in recipients of at least one known HLA antibody-positive component will be about 14.6 per 1,000, while the corresponding estimate in recipients of at least one known HLA antibody-negative component will be about 7.9 per 1,000.

E. Significance

TRALI is now the leading documented cause of transfusion-related morbidity and mortality in the US. The transfusion community has begun implementing measures to reduce the risk of TRALI with a recommended deadline by the AABB of November 2007 for plasma components

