margin is added to account for deaths of patients within six hours of transfusion, missing records, outdate or loss of the distributed products before transfusion or other unforeseen factors. Therefore, the total number of components traced to participating hospitals will need to be 2,590 (1,175 + 118 = 1,293 rounded to 1,295 case and similarly 1,295 control). Control donors will be gender and parity frequency-matched with the antibody positive donors. Additionally, the antibody status of all the available donors who are involved in any TRALI cases found in our study will be determined following a standardized protocol for donor investigation at the participating REDS-II blood centers. A similar procedure will be conducted for control cases.

F2. Management of TRALI cases that are previously reported to the hospital blood bank: It is possible that the hospital blood bank may have received a report of suspected TRALI in recipients of the study units. These reported cases will also be identified during record review and will be subject to the same rigorous process described in this protocol to establish or reject a diagnosis of TRALI. Only those cases that meet the diagnostic criteria of this protocol for TRALI will be included in determining the prevalence of TRALI.

F3. Radiology report/digital image capture and review: Retrospective data collection procedures will include an initial review of radiology data to ascertain if a chest x ray was done within 24 hours of the transfusion. If yes, the post-transfusion chest x-ray will be reviewed and a written verbatim radiologist's interpretation will be recorded in the data collection form. If available, a pre-transfusion chest x-ray will also be reviewed and a verbatim report will be recorded in the data collection form. If more than one radiology report for chest x-ray exists within 24 hours of the study unit transfusion, all the reports will be captured in the data collection forms. Those patients with new or worsening bilateral lung infiltrates, pulmonary edema, or ARDS, will have their data forms forwarded to the local REDS-II investigator for review.

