F5. Triage critical care physician review: Based on these considerations, the number of charts that would require a review by a triage critical care specialist will be 311 (60% of 518). The triage physician would receive the case summaries in the form of several PowerPoint slides per case along with the detailed medical chart data consisting of completed extended data form for each case and digital images of chest x-rays. The triage MD will be blinded as to the type of study component transfused. The review will be performed by a single MD and all REDS-II Centers will send records for review to the triage MD. The major aspect of this review is to determine if there is sufficient information to conclude that the patient has moderate to severe TACO. If such is the case, the triage MD will complete the form indicating the presence of TACO and no further reviews will be required. The number of cases that will be excluded from further review by the triage MD is uncertain, but may amount to 50%. If the percent is lower, then the workload for the Medical Review Board may need to be reassessed during the conduct of the study.

The above described processes are shown in the flow chart on next page and in Table-4 below.

Parameter	Number of patients	Comment
Number of patients needed for	1175	Based on 90% power calculations, for
each study arm		each arm of the study
Including ten percent margin	1,275	Margin added to account for missing
		records, deaths within six hours etc.
Total number of patients	2,590	Two equal groups of antibody positive
		and antibody negative component
		recipients
40% of patients with a post-	1,036	No. of post-transfusion chest x-rays
transfusion chest x-ray		needing a review
20% of patients with a pre-	518	No. of patients with a pre-transfusion
transfusion chest x-ray		chest x-ray
Total number of chest x-rays	1,554	No. of chest-rays needing a review

Table-4: The stepwise approach to record review with corresponding estimated activity numbers for the five REDS-II Centers

50% of post-transfusion chest x- rays showing new or worsening bilateral infiltrates/pulmonary edema	518	No. of patients requiring hypoxemia determination review
60% of the study patients would have hypoxemia	311	No. of patients with evidence of hypoxemia

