F21. Medical Board for adjudication (aka Expert Panel): A Medical Board will be created by the Coordinating Center and will be composed of three physicians that will be qualified by training, certification, and/or experience as critical care specialists, pulmonologists, and/or intensivists. The Board will review submitted data without the knowledge of HLA antibody status of the transfused blood components. Two members of the Board will review each case and if there is an agreement regarding diagnosis, the case will be assigned the agreed upon diagnosis. If there is a disagreement between the members, then such cases will be discussed during periodic conference calls of the Board to arrive at an adjudicated diagnosis. These conference calls may be attended by the REDS-II investigators. The Board will be asked to make a determination of the case as: 1. TRALI: classified by whether or not other risk factors for acute lung injury are present or not; 2. Acute lung injury (ALI); 3. Transfusion-related cardiac overload (TACO); 4.TRALI/TACO (overlap cases); and 5.Other (e.g. transient hypoxemia due to transient airway obstruction at bronchoscopy or extubation or other causes of transient hypoxemia). These categories will allow cases to be grouped either by the Canadian Consensus Conference definition or the NHLBI Working Party definition, which differ only slightly. For cases that are assigned a diagnosis of other, the Board may be able to assign a more specific diagnosis such as Febrile Non-Hemolytic Transfusion Reaction (FNHTR), bacterial sepsis, etc. Each member of the Board will record their diagnosis on the Expert Review Log Form (Appendix I) and fax it to the coordinating center.

F22. Deaths identified during record review: If during hypoxemia review or detailed chart review, deaths occurring within 24 hours after completion of the study unit transfusion are identified, they will be recorded in the data collection form along with the reason/cause of death. This will occur whether or not the case goes on to further record review. Such deaths along with deaths occurring within 24 hours of transfusion of the study unit in which TRALI, TACO or other serious adverse transfusion reaction is a possibility will also be recorded in the data collection form.

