A list of the components that were supplied to each participating hospital will then be printed by the blood center and provided to each corresponding transfusion service medical director or designated individual to identify corresponding recipients and to have the radiology and the medical records be abstracted by the record review coordinator(s). All information will be tracked and compiled into the tracking and data management systems either directly by research staff at the blood center/blood bank or by Westat, if forms are mailed to the coordinating center for data entry.

The coordinating center will be responsible for formation of the medical review board. The medical review board will assess all completed data forms in a blinded manner to determine the presence or absence of TRALI as described above. The coordinating center will compile the results of these reviews into the data management system to allow for formation of a database that will be used for analyses. The proposed diagnostic criteria for TRALI are detailed in the next section.

F25. Proposed Diagnostic criteria for TRALI: Using the Canadian Consensus Conference criteria, the medical review board will be responsible for reviewing the completed recipient forms and determining the presence or absence of TRALI (Kleinman et al).

- 1. New hypoxemia must be present and hypoxemia is defined as pO2/FiO2 ratio of <300 within 6 hours of completion of transfusion or venous oxygen saturation (SpO2) of less than 90% on room air; or other clinical evidence of hypoxemia (e.g., cyanosis). Based on the recent report from Rice TW et al., additional criteria to determine hypoxemia representative of ARDS will be included as follows: ratio of SpO2/FiO2 <315; where FiO2 will be calculated for patients receiving oxygen by cannula or mask as follows: 1 liter = 0.21; 2 liters = 0.23; 3 liters = 0.25; 4 liters = 0.3; 5 liters = 0.35; 6 and 7 liters = 0.45, and 8,9, and 10 liters = 0.49 (Rice TW 2007).
- 2. Bilateral infiltrates on frontal chest radiograph (obtained within 24 hours of Completion of transfusion) must be present. There must be absence of left atrial hypertension (i.e., circulatory overload). However, if ALI is diagnosed by the expert panel in the presence of left atrial hypertension, the case may be classified as TRALI/TACO (overlap case).

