HLA antibody prevalence in blood donors*	Percent of TRALI that are antibody mediated**	Average # components per transfusion episode***	'control' r	Number required in each of 'case' and 'control' recipients arms for different power estimates		
			80%	85%	90%	
8.5%	80%	6	806	917	1067	
9.0%	80%	6	886	1007	1175	
10.0%	80%	6	1034	1178	1379	

* Results for LAPS show the HLA prevalence to be about 16% for women and about 1% for men, hence overall prevalence of HLA antibodies in units transfused in hospitals participating in LAPS-II is likely to be in the range of 8.5% to 10%.

** Approximately 80% to 85% of TRALI cases are thought to be antibody mediated. The required sample size decreases as the immune mediated percentage increases, thus conservatively 80% is used in the table.

*** Recipients receiving an apheresis component are assumed to receive no other components during the transfusion episode. Recipients receiving an FFP (or other plasmas) component are assumed to receive on average a total of 6 components during the transfusion episode, and as a worst case scenario the additional components are assumed to be high risk TRALI components.

H4. Sample size and power selected for the study: From the above table and the details provided in Appendix D, the sample size selected was 1,175 for the antibody positive components and 1,175 for the antibody negative components. This number will give 90% power to detect a TRALI rate difference between the two groups of recipients. This conservatively assumes that a transfusion episode consists of 6 components although apheresis platelet component transfusion is most often a single unit transfusion episode. The percentage of TRALI that is antibody mediated is assumed to be 80% which may also be a conservative estimate. To the above number, a 10% margin is added to account for missing records etc. Therefore, the total number of antibody positive and antibody negative components is 1,295 for each group.

Based on OSMB recommendations we plan to conduct an interim analysis to see if the estimated sample size is adequate. The interim analysis will assess the average number of components per transfusion episode (assumed to be 6) and the TRALI incidence per component of unknown HLA status (assumed to be 0.18%). If the average is much greater than 6 or the incidence much lower than 0.18%, then increasing the sample size will be considered. A detailed description of the interim analysis is provided in Appendix H.

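### F1 and Table-4 plan deaths within six hours of transfusion as losses, although six hours is the TRALI onset window and other sections keep these recipients in the study

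*Protocol*

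**What the plan says.** F1 sets 1,175 reviewed recipients per group and adds 10%. The "margin is added to account for deaths of patients within six hours of transfusion, missing records", product outdate or loss, and other unforeseen factors. The arithmetic is "1,175 + 118 = 1,293 rounded to 1,295 case and similarly 1,295 control". Table-4 gives the same reason in its comment on the margin: "records, deaths within six hours etc". H4 describes the margin without naming deaths: "To the above number, a 10% margin is added to account for missing records etc".

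The same six hours defines the outcome. G1 states that "symptoms of TRALI must occur within 6 hours of the transfusion", and criterion 1 of F25 looks for hypoxemia "within 6 hours of completion of transfusion".

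Other sections treat early deaths differently:
- Section I includes all recipients of study components at participating hospitals, with no survival condition.
- Section J lists exclusions for donors only.
- F22 opens with "If during hypoxemia review or detailed chart review, deaths occurring within 24 hours after completion of the study unit transfusion are identified" and has these deaths recorded with their cause, whether or not review continues. Its last sentence adds deaths within 24 hours in which TRALI, TACO or another serious reaction is possible.
- H6 and the draft letter in Appendix B say what to do with fatal TRALI that the study finds.

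Section E gives mortality as part of the rationale: "TRALI is now the leading documented cause of transfusion-related morbidity and mortality in the US".

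**The concern.** A missing chart or an outdated unit can reasonably be taken as unrelated to TRALI. A death inside the onset window cannot. Grouping the three as losses to be made up by numbers treats a possible outcome as a missing observation. Replacing such recipients with survivors restores the count but not the events.

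The primary comparison is at stake to some degree, and so are the absolute incidences per recipient and per unit that Section L plans to report. G1 discusses missed mild cases and late films and concludes that no significant number of TRALI diagnoses will be missed. It does not consider rapidly fatal cases.

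**Working it through.** **1. The plan's own figures.** Inputs are the rates of 2.32% and 0.79%, 1,175 per group and a one-sided 0.05 exact test (Appendix D), with Fisher's exact test as the primary analysis (Section L). Exact power is the sum of the binomial probabilities of all 2x2 tables that the one-sided Fisher test rejects. It is 90.0% at 1,175. At 886 and 1,007 it is 80.0% and 85.0%, which matches the 9% row of Table-12. The stated design reproduces.

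**2. The margin.** 1,175 x 0.10 = 117.5, taken as 118; 1,175 + 118 = 1,293, rounded to 1,295. The allowance is 1,295 - 1,175 = 120 per group for all reasons together. The share expected from early deaths is not given.

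**3. Are margin recipients in or out?** F1 and Table-4 imply that they do not contribute to the 1,175. F23 projects 30 and 10 cases from the full 1,295 (1,295 x 0.0232 = 30.0; 1,295 x 0.0079 = 10.2), as if all contribute. Sections I and J give no ground for removing them. The protocol does not say how a six-hour death is counted.

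**4. Path of an early death through the forms.**
- The blood bank part of the Screening Form has a transfusion-reaction field but no death field.
- The form stops if there is no chest film within 24 hours after issue.
- Discharge status (alive or deceased) is first asked on the Extended Data Collection Form, which is reached only after the x-ray screen.
- The hypoxemia and detailed reviews that trigger F22 also follow that screen (C1, F3, G1).
- F22 requires recording and does not ask for adjudication.

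**5. Direction of the bias.** Let p be the true TRALI risk, f the share of TRALI that is fatal within six hours, and d the share of all recipients who die within six hours. If six-hour deaths are set aside, the rate among those left is p(1 - f)/(1 - d). This is below p whenever f exceeds d, that is, when recipients with TRALI are more likely than others to die that early.

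**6. Size, by assumption only.** The documents give neither f nor d. Take f = 5%, 10% or 20% in both groups, ignore d, and keep 1,175 per group. Events lost are f x 1,175 x p.

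| f | Rates left (case / control) | Events lost (case / control) | Difference in rates | Power |
|---|---|---|---|---|
| 0 | 2.32% / 0.79% | 0 / 0 | 1.53 points | 90.0% |
| 5% | 2.20% / 0.75% | 1.4 / 0.5 | 1.45 points | 88.5% |
| 10% | 2.09% / 0.71% | 2.7 / 0.9 | 1.38 points | 86.7% |
| 20% | 1.86% / 0.63% | 5.5 / 1.9 | 1.22 points | 82.4% |

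The rate ratio stays at 2.32/0.79 = 2.9 in every row. What falls is absolute incidence, by the factor 1 - f, and with it the difference and the power.

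**The case against.** A reader might infer that the plan drops rapidly fatal TRALI from both numerator and denominator. The documents do not support that. A margin is a planning allowance and not an exclusion rule, and no passage removes an early death from the analysis. A recipient with a qualifying film and hypoxemia goes to the triage physician and, unless TACO is diagnosed, to the Board, alive or dead. F2 puts suspected TRALI already reported to the blood bank through the same process.

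Nor can one say that a death without a film is never recorded. The last sentence of F22 is not limited to the later reviews, and F16 has the blood bank note adverse events reported within 24 hours of issue. But neither form as reproduced gives that sentence a place before the x-ray stop, and the blood bank route reaches only events that someone reported.

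A death before any film cannot meet F25, which requires bilateral infiltrates, so better capture adds no primary TRALI cases from that group. This stands, and it is why such deaths should be reported separately and not counted.

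The power losses rest on assumed fractions and suppose that every early fatal case is lost, including those with films. If nothing is lost, all 1,295 per group give 92.6%. A reader might also infer a loss confined to the case group, but nothing in the documents points to that. The blinded sample size review in Appendix H could respond to a low overall incidence, though not to the bias.

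Counting rules can be left to a statistical analysis plan. The conflict between F1, Table-4 and Section I lies in the protocol itself, however, and no analysis plan can recover a death that the form did not capture.

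**Conclusion.** The point holds as a contradiction about who is evaluable, together with a gap in capture. F1 and Table-4 plan six-hour deaths as losses in the window where the outcome occurs, while Sections I and J, H6 and Appendix B keep them in. If the losses reading is followed, the loss depends on the outcome and a larger sample cannot correct it. Absolute incidence would then be biased downward, provided that recipients with TRALI are more likely than others to die within six hours.

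The size is unknown. The fall to 88.5%, 86.7% or 82.4% power is a sensitivity range under an assumed equal fractional loss in both groups, not an estimate. Under that assumption the rate ratio is not distorted.

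**What to change.** - **F1 and Table-4:** remove deaths within six hours from the reasons for the margin, and state that these recipients remain evaluable and in the denominator, in line with Sections I and J.
- **Screening Form:** add death within 24 hours, with date and time, for every recipient, placed before the stop for no post-transfusion film.
- **F22:** send each six-hour death that has any post-transfusion film or oxygenation data through the existing triage and Board review, and count those that meet F25.
- **Reporting:** give by arm the number of six-hour deaths that cannot be classified for lack of a film, without counting them as TRALI in the primary analysis.

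The cost is wording in three places, one form item, a few extra chart reviews by reviewers already in place, and some unclassifiable deaths to report. The whole margin is 120 per group for all reasons, so the plan itself expects fewer early deaths than that. The form change should precede abstraction: charts that stop at screening go no further, and F18 has the link to the patient destroyed at the end of the study.
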